	 A carer of a young person who has not consented to take part in the study.
Summary of	Mindfulness for Adolescents and their Carers (MAC)
trial	MAC consists of eight, weekly, group-based sessions of between 1 hour 30 minutes and 1
intervention	Nindfulness Record Cognitive Therapy (MRCT) is a NUCE recommended treatment for
	recurrent depression (Kuyken et al. 2016) (Kuyken et al. 2016). A similar mindfulness-
	hased intervention could be efficacious for depressed adolescents, but we currently lack
	evidence (Dunning et al., 2022)(Dunning et al., 2022). We have adapted MBCT specifically
	for adolescents with depression. Key features of our intervention include theory-driven
	targeting of maintenance factors and a parallel group intervention for the young people's
	parents or carers.
Intervention	8 sessions over 8 weeks
duration	
Follow-up	Young people will also be invited to complete the short form (13 items) of the Moods and
duration	Feelings Questionnaire (SMFQ; (Angold et al., 1995)(Angold et al., 1995) fortnightly via a
	web-based outcome measurement system. Follow up data at 14 weeks and 12-months
	post-randomisation will also be completed (see Figure 5).
RCT	WP3 (RCT) + WP4 (Investigating patients' experience and testing moderators and
duration	mediators of treatment effects) will:
	recruit from June 2024 to December 2025,
	 with the final cohort of 12-month follow-up assessments occurring in December
	2026,
	 with an internal pilot and a Stop-Review-Go checkpoint in March 2025 (see Figure 10).

Outcome	Primary Outcome: Short Moods and Feelings Questionnaire (SMFQ) (Angold et al.,											
Measure	1995)(Angold et al	l., 1995) completed	at fortnightly interva	als from rar	ndomisatior	n until 12						
Wiedsure	months post randomisation.											
	We intend to estimate the difference in AUC by including an intervention arm by fortnight											
	interaction term, allowing the extraction of fortnightly/follow-up visit intervention arm											
	difference estimates, and then the calculation of the appropriate linear combination of											
	these estimates (i.e. using the trapezium rule).											
	Other outcomes are listed in the summary table below, with full details provided in the											
	main body of the protocol.											
	Construct	Young People	Parent/Carer	Timepoin	Timepoint Data Collected							
		Completed	Completed									
		•	•	T0: B/L	T1:3.5m	T2:12m						
					F/U	F/U						
	Eligibility											

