- **Remote.** We will include people who prefer remote treatment from all six geographical sites and then randomise them to the different treatment arms. This opens the treatment to those who may struggle with face-to-face or otherwise choose not to join. Our PDG necessarily involved remote delivery as it ran during the Covid-19 Pandemic. Some young people and parents expressed a strong preference and our advisory groups recommended that we retain this option for the PGfAR. We will therefore deliver one remote group with each cohort, randomising those who express a preference for this mode of delivery from all the sites. Administratively, it will be treated as an additional site.

The pilot would commence in June 2024, involving each of the pilot sites delivering two MAC groups, one in the Autumn 2024 and one in the Spring 2025. Providing we meet the STOP/REVIEW/GO criteria in Spring 2025, the final two trial sites will open for recruitment and all six sites will deliver two MAC groups, one in Autumn 2025 and one in Spring 2026 (see Figure 11). The remote option will recruit from all sites and run in parallel.

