Following written consent, participants will be randomised in a 1:1 ratio to one of the two treatment arms (TAU, or MAC + TAU). A web-based randomisation system will be designed, using the bespoke KCTU randomisation system. The randomisation system will be created in collaboration with the trial analyst/s and the CI and maintained by the King's Clinical Trials Unit for the duration of the project. It will be hosted on a dedicated server within KCL. The system will employ block randomisation with randomly varying block sizes and will be stratified by i) site, ii) if the young person is taking a therapeutic dose of antidepressants or not and iii) if their RCADS (Ebesutani et al., 2012) score at baseline indicates that they have severe depression or not. The details needed for randomisation will be held in a dedicated database. Only the Programme Manager, Trial Manager and Programme Administrators (unblinded) will have access to the randomisation system (or their nominated backup in times of absence; the nominated backup will not be another member of the blinded team but will be a team member whose role on the delegation log specifies this role as contingency Trial Manager).

Sample size calculation

Our power calculation suggests that 480 participants (240 per arm, MAC allocation=20 groups) will allow us to detect an effect size of 0.3 with 90% power, allowing for 20% attrition. The calculation assumed using a two-sided independent samples t-test of the difference between arms, alpha = 0.05, assuming a MAC group size of 12, intraclass cluster correlation of 0.05, i.e. a design effect / inflation of $1 + [12 - 1] \times 0.05 = 1.55$ (Williams et al., 2008), one baseline and two post-randomisation measures with correlation rho = 0.5 = deflation factor of 0.5 (Machin et al., 2009), and 20% attrition (Kennard et al., 2009;(Mental Health Taskforce, 2016). The calculation was done using the Gpower software, with methods from Killip et al used to hand-calculate the cluster effect for MAC group (Killip, 2004).

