19. TRIAL TIMELINE

The study will start with an internal pilot RCT of two groups in each of the four sites (East of England, London, Devon, and Sussex) and one remote group; groups will be run in the Autumn 2024 and Spring 2025 academic terms. Should we meet our STOP/REVIEW/GO criteria, the full RCT would then bring on two additional sites (Oxford and Nottingham) and run a further 2 MAC groups in all six sites plus a remote group during the Autumn 2025 and Spring 2026 terms. Eight to twelve weeks are allowed for recruitment, and randomisation will occur within a month of the groups beginning. We have deliberately avoided running MAC groups during the summer terms since our experience indicates poor uptake while young people are preoccupied by examinations (see **Figure 10**).

Participants' levels of depression will be measured using the SMFQ for young people and PHQ-8 for parent/carers fortnightly for 12 months following randomisation. All participants will also complete a full set

of measures at baseline, just after the MAC finishes (14 weeks post-randomisation) and 12 months post randomisation. Further details of how this work fits with the rest of the programme from the timeline are included in the Gantt chart (**Figure 11**)

Figure 10: RCT Milestones

2027: ECONOMIC MODELLING, MECHANISMS, ANALYSIS, DISSEMINATION

Figure 11: Whole Programme Gantt

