20. CRITERIA FOR EARLY TERMINATION OF THE TRIAL

The trial has the following stop-review-go criteria based on recruitment, uptake of intervention, and drop out, that may lead to premature discontinuation of the trial.

STOP / REVIEW / GO criteria:

- 1. Mean recruitment of 40 adolescents per geographical site (target 48, stop if < 36),
- 2. Mean of 9 adolescents commence MAC from each site for each cohort of groups (target 12, stop if < 6),
- 3. Mean of 36 adolescents complete SMFQ at 3 months per site (target 40, stop if < 28).

Values in the review zones (36-39 recruited, 6 to 8 commenced, 28-39 retained) would require exploration for the potential to improve and continue with advice from the funders and the Trial Steering Committee.

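### The 3-month retention criterion is a raw count that needs both pilot cohorts, so at a March 2025 checkpoint it can read STOP or REVIEW with no drop-out

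*Protocol*

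**What the plan says.** Section 5 (RCT duration) places the decision in the calendar: "with an internal pilot and a Stop-Review-Go checkpoint in March 2025". Section 10 is looser and says that, subject to the "criteria in Spring 2025, the final two trial sites will open for recruitment".

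Each pilot site delivers two MAC groups, "one in the Autumn 2024 and one in the Spring 2025"; section 19 repeats that "groups will be run in the Autumn 2024 and Spring 2025 academic terms". Section 19 also states that "randomisation will occur within a month of the groups beginning", and places the first full follow-up "just after the MAC finishes (14 weeks post-randomisation").

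Section 20 gives three criteria. Criterion 1 is recruitment per geographical site: 40, with a target of 48 and a stop below 36. Criterion 2 counts adolescents starting MAC and is worded per cohort of groups. Criterion 3 is retention: "Mean of 36 adolescents complete SMFQ at 3 months per site (target 40, stop if < 28"). It is not worded per cohort and does not mention participants who are due. The same section lists 28 to 39 retained as the review zone.

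**The concern.** A retention criterion should separate a pilot that keeps its participants from one that loses them. Criterion 3 counts completers, so a participant who has dropped out and one whose 3-month date has not arrived lower the count equally. The count needs a contribution from the second cohort, whose groups run in the same term as the checkpoint.

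Section 20 says the criteria may lead to early discontinuation, and section 10 makes meeting them the condition for opening the last two sites. A STOP or REVIEW reading produced by the calendar would leave the committee either acting on a false signal or devising a different rule after seeing the data.

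**Working it through.** **Inputs from the protocol.** Two pilot cohorts per site (sections 10 and 19); the sample size is calculated "assuming a MAC group size of 12" and allocation is 1:1 (section 15); thresholds from section 20.

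**Reproducing the target.** 2 cohorts × 12 per MAC group × 2 arms = 48 per site, which matches the recruitment target in section 20. Each cohort therefore contributes 48/2 = 24, or 40/2 = 20 if recruitment only reaches the go value of 40.

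**How much of the spring cohort must be due, with zero drop-out:**

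| Recruited per site | Autumn alone | Spring needed to leave STOP (28) | Spring needed to reach 36 |
|---|---|---|---|
| 48 | 24 | 28 − 24 = 4 of 24 (17%) | 36 − 24 = 12 of 24 (50%) |
| 40 | 20 | 28 − 20 = 8 of 20 (40%) | 36 − 20 = 16 of 20 (80%) |

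**Latest randomisation date.** The protocol does not define 3 months for this criterion. Week 12 (84 days), 90 days and the 14-week visit (98 days) are all possible. To be due by 31 March 2025 a participant must be randomised by 6 January 2025, 31 December 2024 or 23 December 2024 respectively. To be due by 1 March the dates are 7 December, 1 December and 23 November 2024.

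**Count at the checkpoint.** Maximum count = autumn cohort + spring cohort × share due, where share due = days in the randomisation window on or before (check date − follow-up days) ÷ 31. Assumptions: the whole autumn cohort is already due, spring randomisation is uniform over a 31-day window, and nobody drops out.

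With 90 days and 48 recruited:

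| Spring randomisation window | 1 March | 15 March | 31 March |
|---|---|---|---|
| 1–31 December 2024 | 24 + 24 × 1/31 = 24.8 (STOP) | 24 + 24 × 15/31 = 35.6 (about 36) | 24 + 24 × 31/31 = 48 (GO) |
| Month to 6 January | 24 (STOP) | 24 + 24 × 9/31 = 31.0 (REVIEW) | 24 + 24 × 25/31 = 43.4 (GO) |
| Month to 13 January | 24 (STOP) | 24 + 24 × 2/31 = 25.5 (STOP) | 24 + 24 × 18/31 = 37.9 (above 36, but in the review zone) |
| Month to 20 January | 24 (STOP) | 24 (STOP) | 24 + 24 × 11/31 = 32.5 (REVIEW) |
| 1–31 January 2025 | 24 (STOP) | 24 (STOP) | 24 (STOP) |

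With 40 recruited, the December window gives 20 + 20 × 1/31 = 20.6 (STOP), 20 + 20 × 15/31 = 29.7 (REVIEW) and 40 (GO).

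**Sensitivity to the meaning of 3 months (December window).** At 98 days and 31 March: 24 + 24 × 23/31 = 41.8 (GO) at 48 recruited, and 20 + 20 × 23/31 = 34.8 (REVIEW) at 40. At 84 days and 48 recruited, 1 March gives 24 + 24 × 7/31 = 29.4 (REVIEW) and 15 March gives 40.3 (GO). For randomisation throughout January, 84 days lifts the 31 March count only to 24 + 24 × 6/31 = 28.6 (REVIEW).

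Retention is 100% in every cell, so a percentage of those due would read 100% throughout.

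**The case against.** A reader might infer that, on the protocol's own timings, most of the spring cohort cannot have reached 3 months by March. The documents do not support that. They give neither a start date for the spring groups nor a day in March. Section 5 ends recruitment in December 2025 and puts the final 12-month follow-up in December 2026, although the last groups run in Spring 2026. That implies a spring cohort randomised by the preceding December. Carried back a year, the Spring 2025 cohort would be randomised by December 2024 and reach 90 days by the end of March. Section 19 agrees: if the 14-week visit falls just after an 8-week course, randomisation comes well before the first session. Even with groups starting on 6 or 13 January, 81% (25/31) or 58% (18/31) of the cohort is due by 31 March at 90 days.

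The looser wording in section 10 also leaves room for a later check, and the milestone figure cited in section 5, which is not shown in the text reviewed, may narrow the date. Nor do the documents describe automatic termination: the criteria may lead to discontinuation, and review-zone values go to the funders and the Trial Steering Committee for advice.

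All of this stands, and it limits the point to a schedule without slack. It does not rescue the rule, because the favourable December reading still gives STOP on 1 March at 90 days and does not comfortably pass on 15 March. A reading in which only the autumn cohort is judged has no support in the text and could never pass, since 24 is below 28.

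**Conclusion.** The point holds in a limited form. Criterion 3 is a raw count that cannot leave STOP without at least 4 of the 24 spring participants per site, or reach 36 without 12 of them, even if nobody drops out. It works as intended only if spring randomisation is complete by about the end of December 2024 and the check is made at the end of March, and the protocol commits to neither. Outside those conditions it can measure calendar position instead of retention. At 90 days with zero drop-out and 48 recruited, the count ranges from 24 to 48 per site across the scenarios tried.

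This rests on 24 per site per cohort, an autumn cohort fully due by March, and uniform randomisation over a month. Randomisation concentrated early in the window would raise the counts. That the autumn cohort alone falls below the stop line depends on neither the spring start date nor the uniform-randomisation assumption.

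**What to change.** - Express criterion 3 as the percentage completing the SMFQ among participants whose 3-month date has passed at a stated data cut, with a minimum number due. The percentage thresholds need choosing: the present pairs imply 40/48 = 83% at target, 36/40 = 90% at the go value and 28/36 = 78% at the stop line, which are not in order.
- Alternatively, keep the counts and date the retention decision after the last spring participant is due. With randomisation to 31 December 2024 the last 14-week date is 8 April 2025; with randomisation to 31 January 2025 it is 9 May 2025. Both precede the Autumn 2025 groups. Criteria 1 and 2 can still be judged in March.
- State whether 3 months means week 12 or the 14-week visit.
- Reconcile March 2025 in section 5 with Spring 2025 in section 10.
- Reconcile the 28 to 39 review zone with the go value of 36, since 36 to 39 currently falls in both.

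The cost is protocol wording. The downside is that one of three criteria is confirmed a few weeks later, or in March on fewer participants and so less precisely.

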6. PLAIN ENGLISH SUMMARY

Background:

In the UK about 140,000 15–19-year-olds experience depression. An estimated 35,000 young people access NHS treatment for depression, of which,

- about 14,000 do not respond.
- A further 8,000 are likely to experience depression again after initial successful treatment.

Teenagers who still have symptoms after treatment for low mood, depression or anxiety, or who relapse quickly, need more treatment options.

These young people have a high risk of substance-misuse, self-harm, school, or relationship difficulty, as well as poor adult mental and physical health. Parenting a teenager with depression is stressful and can damage family relationships. Teenagers whose parents have depression are more likely to develop mental health problems in adulthood.

Mindfulness-Based Cognitive-Therapy (MBCT) combines training in mindfulness meditation with principles from cognitive therapy. It teaches skills to recognise early warning signs of depression, avoid repetitive thinking patterns that make depression more likely, and respond in ways that protect mental health. Although MBCT is recommended for adults who have experienced three or more depressive episodes, MBCT for teenagers is relatively untested.

We developed Mindfulness for Adolescents and Carers (MAC) as a version of MBCT adapted to be more engaging for teenagers. MAC aims to help teenagers recover from depression and the parallel parent/carer group aims to support parents and carers to cope better.

Aims:

We want to see if MAC supports recovery and prevents relapse amongst 15-18-year-olds who risk developing recurrent depression as adults.

Methods:

Our research has work packages as follows:

- 1. Finalise our therapist-training programme.
- 2. Co-produce two Apps to encourage and measure mindfulness practice.
- a) Recruit 480 teenagers, and their parents/carers will be invited too. Half will access MAC and half will access the standard NHS treatment currently available. This will allow us to compare the differences between the two groups on depression and other outcomes.
 b) Compare the two group's treatment costs, with their symptoms 9 months after treatment, to assess whether MAC is value for money.
- 4. Find out how MAC works and who benefits the most by exploring changes in how teenagers and parents feel, think, and relate to each other.
- 5. Understand how best we can scale up MAC across the NHS.

This protocol refers to work packages 3 and 4 only.

Public and Patient Involvement and Engagement (PPIE):

- Young people and parents with experience of MBCT designed the MAC materials and helped to design our research.
- Two co-applicants with lived experience and our PPIE lead will coordinate PPIE throughout the Programme.
- We will recruit 3-4 young people to join them as well as establishing the Research Advisory Groups of young people and parents.
- Each part of the programme will have dedicated support from 4 young people with lived experience.

Dissemination:

We will share our findings with different audiences. Examples will include blogs, podcasts, videos, social media, websites, and both self-help and professional networks.

7. PATIENT AND PUBLIC INVOLVEMENT

[name] and [name] were co-applicants on the Programme Development Grant (PDG) and core members of the PDG project team, attending monthly meetings to discuss progress and future development. They have met with the research team intermittently over a period of six years and have been integral in the

development of the manual for MAC and all our feasibility studies. They have assisted and advised on who should be referred into the groups and how they should be approached, how the study should be explained, what are the most important outcomes to measure, which questionnaires ask the most appropriate questions and what is the most appropriate comparator.

In addition, we sought advice about the PDG from CAMHS advisory groups at the Institute of Psychiatry, Psychology and Neuroscience and South London and Maudsley NHS Trust as well as our Devon based advisory group to broaden the diversity of our advisers. These sessions focused on adaptations to MAC in relation to remote working and whether these should remain in the trial, and a discussion of our findings and next steps.

[name] became involved in this application at Stage 1 of the current application. She has supported [name] and [name] in developing the PPIE programme of work. [name] and [name] have attended the programme development meetings and actively contributed to decisions about study design well as writing the PPIE sections of the application.

[name], [name], and [name] will form the core PPIE leadership group. Each WP has a clearly defined PPIE element and representative lead. [name] will co-ordinate and support all the PPIE work and representatives, and a formal communication plan created. Work package leads will also be responsible for updating the core team and PPIE will be a standing item on monthly whole team meetings.

We are recruiting to two diverse Research Advisory Groups (RAG) of experts by experience, one composed of parents or carers and one of young people in the age range 14 to 18. They will advise researchers on approaching potential participants and be involved with core group training, interpretation of results, dissemination advice, and coproduction of dissemination materials. We intend to over recruit to the RAGs, aiming to have a rolling membership of 12 people in each RAG, so that people with lived experience can vary the extent of their commitment over the research programme as the other demands on their time and availability vary. We realise that people are busy, and their circumstances will change during the Programme and want to be able to accommodate this whilst ensuring continuity of PPIE activities. Fluctuating availability is particularly an issue for young people, who are likely to face public examinations and major transitions, such as leaving home for college or work over the course of the programme.

All PPIE time and travel expenses for face-to-face meetings have been costed. Recruitment will be through multimedia (both online and offline methods), as well as through our clinicians, such as previous MBCT groups attendance, CAMHS, or through local contacts. The PPIE Lead will give full support and will arrange any individual's needs (accessibility, training etc). Examples include 'zoom' practice calls and glossary/dictionary provision. Private computers in a local library can be booked for those not able to meet from home.

8. BACKGROUND

The problem

The prevalence of depression among young people increased during the previous two decades (Sadler et al., 2017) with further evidence of deterioration in young people's mental health in the UK since the onset of the Covid-19 pandemic (Newlove-Delgado et al., 2021). Prevalence estimates vary depending on the age, population, and methods used, the time- period studied, and impairment criteria applied. A pre-pandemic meta-analysis of 41 studies in 27 countries suggests that the world-wide prevalence of depression was 1.7 to

3.9% (Polanczyk et al., 2015) among children and young people under the age of 18 years, while a 2021 meta-analysis of 29 studies from 11 countries provides an alarming estimate of 21.2 to 29.7% in the same age group (Racine et al., 2021). In the latter study, prevalence estimates were higher in data collected later in the pandemic, as well as among girls and older teenagers. Mental health conditions cost the UK economy almost £18 billion per year in 2019/2020, emphasising the potential of prevention (Mcdaid et al., 2022).

Young people who function poorly in their mid-to-late-teens pay a heavy developmental price as education, occupation and child-bearing related decisions during these years can drastically alter life trajectory. In this developmental period, young people often develop attitudes and habits in relation to diet, exercise, sexual activity, and substance use that profoundly influence future health (Sawyer et al., 2012). Depression in adolescence predicts school-failure, substance-misuse, self-harm, and poorer occupational function, as well as poorer adult mental and physical health, particularly among young people who experience repeated episodes (Costello & Maughan, 2015). Insufficient treatment response significantly increases the risk of relapse (Costello & Maughan, 2015; Weisz et al., 2017), while between 34% and 75% of young people relapse within five years. Each depressive episode also increases the risk of subsequent recurrence (Costello & Maughan, 2015).

Mental health interventions for young people are underexplored, particularly for anxiety and depression, which has become a major focus of research funders (Dubicka & Bullock, 2017; Mental Health Taskforce, 2016). Treatment non-response and residual symptoms strongly predict recurrent depression among young people, yet current evidence on relapse prevention has been researched mostly following full initial recovery (Cox et al., 2012; Kennard et al., 2009). The Cochrane review of relapse prevention in young people reported that medication reduced the proportion who relapsed from two-thirds to 40% (Kennard et al., 2009), while psychological approaches were less frequently studied and showed similarly modest effects.

Effective methods to treat residual symptoms and prevent relapse are therefore critical, which is why they are listed among the top 10 priorities for depression research according to the James Lind Alliance (Mehta et al., 2014; Mental Health Taskforce, 2016; Weisz et al., 2017). In addition to the alleviation of psychological distress to young people and their families, recovery and its maintenance during adolescence could improve educational, occupational, and social outcomes as well as their health in adulthood. Furthermore, our feasibility work suggests potential "spillover" effects on the mental health of parents, with potentially substantial cost-savings across all public sector services ([name] et al., 2020; Racey et al., 2018).

Existing evidence

A large body of evidence demonstrates that maladaptive responses to negative mood, such as rumination or worry, may be key mechanisms in the onset and maintenance of depressive symptoms (Schäfer et al., 2017). Analyses suggest that poor mental health relates to both a general psychopathology factor, best understood as a reflection of the extent of impairment or dysfunction in a person's life, and a bi-factor model, which includes an internalising psychopathology factor characterised by an increased propensity to respond to stress and negative mood with maladaptive repetitive thinking (Caspi et al., 2014; Farb et al., 2018). Such responses are likely to become increasingly automatic and habitual with recurrent exposure to symptoms of depression and may drive relapse. Interventions that improve the young person's ability to respond adaptively to stress and negative mood may thus be key to fostering recovery, although there is little research into mechanisms in this age-group.

Mindfulness-based Cognitive Therapy (MBCT) is a NICE-recommended treatment for recurrent depression in adults (Kuyken et al., 2016). It was designed to prevent depressive relapse by reducing unhelpful ways of reacting to stress and negative mood, including maladaptive patterns of repetitive thinking; it comprises an

20 WP3+4 Study Protocol, **Version 1.3**, 20.6.24

8-week group-based programme that combines mindfulness practice with cognitive behavioural elements (Kuyken et al., 2016). MBCT aims to teach people to recognise these patterns and to respond in more adaptive ways. There is now a substantial body of evidence for its effectiveness and cost-effectiveness in relapse prevention for depression among adults (Kuyken et al., 2016); with evidence suggesting that the preventative effects of the intervention are increased among people who are suffering from residual symptoms. Importantly, research shows that the utilisation of core skills is maintained, and often increases, after the completion of MBCT, which suggests a lasting potential for buffering responses to negative mood and stress (Farb et al., 2018).

There is an increasing interest in MBIs for children and young people, although enthusiasm is running ahead of the evidence (Dunning et al., 2022). A recent meta-analysis of 68 randomised controlled trials of universal and targeted Mindfulness-based Interventions (MBIs) with under- 19s reported tentative evidence for improved anxiety/stress and social behaviour, but also considerable heterogeneity in interventions, populations and outcomes, plus moderate risk of bias (Dunning et al., 2022). Moreover, the 23 trials that tested MBIs as a targeted or indicated intervention were small, included heterogeneous conditions, and failed to follow-up beyond the intervention. MYRIAD, the largest and most rigorous included study, reported that a universal school-based didactic curriculum delivered to 12- to 15-year-olds did not prevent depression or improve well-being but did improve school climate and reduce teacher burnout (Kuyken et al., 2022). Exploratory subgroup analysis suggested that older teenagers, those practising mindfulness skills and those taught by the most competent teachers may have derived benefit and the investigators recommended that future research should explore indicated MBCT with young people who choose to engage (Montero-Marin et al., 2022). The investigators also suggested that future research would need to consider in more detail the impact of contextual and implementation factors on programme outcomes (Kuyken et al., 2022).

Adaptation of MBCT for young people needs to accommodate the contributing factors specific to adolescent mental health in order to optimise treatment response. How young people cope is strongly influenced by their family context for many reasons; indeed, we have demonstrated a bi-directional relationship over time for depression between parents and children (K. Wilkinson et al., 2021). Given the evidence for intergenerational transmission of depression (Hammen et al., 2012), working with both parents and adolescents may amplify the effectiveness and cost-effectiveness of an intervention to support recovery from depression among those vulnerable to recurrent episodes.

Drawing on the above evidence and theory, we have developed and piloted the MAC programme for young people who have completed a first line psychological intervention for depression or anxiety within CAMHS with a parallel version of the intervention for carers. In our feasibility work, more than half the attending carers had a personal history of depression, and approximately a quarter of whom were taking antidepressants (Racey et al., 2018). Parent involvement was strongly endorsed by young people, carers, and the referring clinicians and, although primarily designed to support young people's mindfulness practice, given its association with treatment response (C. Crane et al., 2014), parents reported that the parallel group supported them through the emotional impact of caring for a child with poor mental health. Carers, as well as young people, reported statistically significant reductions in rumination and improvements in self-compassion and de-centring (Racey et al., 2018). A parallel group for carers would seem to be a particularly powerful approach to support recovery from depression among highly vulnerable young people who have relapsed or not responded fully to initial treatment, and for whom intergenerational transmission is likely to have played a significant role in their presentation. It may also improve carer mental health (K. Wilkinson et al., 2021).

As summarised above, we consulted Young People's Mental Health Advisory Groups in Exeter and London and gathered qualitative information from participating young people and carers during our PDG and feasibility work. We developed and delivered a training programme for CAMHS practitioners to teach MAC. Newly trained practitioners delivered MAC in our pilot trial: and we demonstrated acceptability and feasibility of MAC and the proposed research procedures. The Covid-19 disruption required remote MAC groups and revealed strong and disparate preferences for remote or face-to-face delivery, which we intend to explore further.

